### Task 4: Review data with patient

*RA: Imagine that your patient completed some progress measures since your last session. Using the Jane Doe practice patient, please review my outcome monitoring data with me.*

## WILLOW Full RCT Therapist Protocol

*Please also demonstrate how you would edit a measure*

- Hovers over individual data points**
- Open chart/table view**
- Open Edit Measure view (click data point to view or navigate there from the Table view)**

RA Prompt: What are the different functions you can use with the graph? How can you view more detail about the data? Can you show me how to view the individual answers? How can you edit answers in the case where your patient accidentally entered the wrong answer?

*[Make sure Therapist know the different ways to Edit Measure]*

### **Task 5: Find a WILLOW tool (Activity Monitoring Worksheet)**

RA: Please demonstrate how to find the Activity Monitoring Worksheet

- Finds the Activity Monitoring Worksheet**

RA: You can find the Worksheets and other resources by going to the bottom of the JITT Library page or from the treatment plan (click Getting Started with Activity Monitoring and then Activity Monitoring Worksheet).

### **Task 6: Find the Bird's Eye View of Behavioral Activation.**

RA: Please navigate to the "Bird's Eye View" of BA.

- Navigates to the Bird's Eye View of BA from either the JITT Library page or the protocol page of the patient setup

### **Task 7: Custom agenda item**

RA: A custom agenda item is something that isn't already a part of the protocol that you are using. Please add a customized agenda item that you might do with a typical depressed client.

- Adds custom agenda item from Patient Dashboard**

RA: You can also add agenda items from the Treatment Plan page like you did for an earlier core competency. But you can only add custom agenda items from the Patient Dashboard.

### **Task 8: Use JITT tools and complete agenda items**

RA: Please demonstrate walking a patient through at least one of the BA therapy tasks on the agenda. Make sure to fully use all available resources. Mark this therapy task as complete when you've finished.

*Also check off all but 3 of the remaining JITT therapy task agenda items. What will happen to the therapy tasks that you did not complete during this session? [\*not a requirement to pass, but something they should know]*

### **Task 9: Homework**

## WILLOW Full RCT Therapist Protocol

*RA: Please create a homework assignment for me, due a week from today, called Activity Monitoring. In the Description of the task, please add that the task should be done every day in a block fashion (morning, afternoon, evening).*

- Creates homework assignment as described**

*In order to minimize any confusion on your patient's end, please make sure to enter any instructions you might have for your patient because they will see only exactly what you enter in these fields and nothing more.*

### Task 10: Session note

*RA: Imagine that you finished a session with a client and now you want to create a session note. How would you do that?*

- Creates a session note**

*RA: the one field that must be filled out in the session notes is the Session Number because a future function in WILLOW will be determining whether the patient is on-track or off-track compared to other patients. You would need to fill in the Session Number in order for that function to work for the client.*

### Task 11: Clearing out completed items

*RA: Imagine you completed your third session with the patient, but were in a rush after the session and did not have a chance to get WILLOW up to date to reflect that. The patient just came in for their fourth session, and you need to quickly clear out past items and have the agenda be updated to the items for this session. Demonstrate how you would do this. [not required to "pass", but something the therapist should know how to do]*

*Creating a session note wipes out completed items from the dashboard so that items for the next session are available*

### Task 12: Log Out and Exit WILLOW

*RA: Please show me how you logout and exit WILLOW.*

- Logs out**

*[Script for therapists who pass]:*

*That's terrific. You have successfully navigated all the WILLOW Core Competencies. You are ready to go!*

*<<Follow the script in the WILLOW protocol for Therapists, starting from Step 9>>*

*[Process for therapists who do not pass]:*

*<<Provide supportive feedback. Emphasize that there is a lot to learn and that's why you are doing this. Convey that you are certain they pick it up; it just takes time>>.*

*<<Ask participant if they would like to go through a few areas now, or if they prefer to do a bit more on their own first. Be responsive to their request.>>*

*<<Before concluding the call, reschedule another time to complete the test.>>*

## Step 9: Ready to Accept Study Patients

**During orientation call for CAU condition and Pilot WILLOW therapists | After Feature Review for WILLOW condition**

You are now ready to receive patients!

After this call, I will send you an email with the link to access the study resource materials. This includes the patient flyer and a handout with information a Study Tracking Sheet that will help you track your study assessment schedule for each patient. It also includes space to record the date of your session with each of your research clients across the 12 weeks that you will meet with them for the study. We will ask you about the session dates in detail during your final assessment so please record the date of the therapy session for each patient each week or indicate if the session that week was skipped. **Please also be sure to record the Care Start Date and let us know what this date is.** The Care Start Date is the first date the patient received services at your clinic; the care start date is your patient's first face-to-face psychotherapy session and includes the intake session. We will be using this date in our study analyses so it is very important that we have this date on record.

Okay, now I'd like to summarize the referral process again so we're on the same page. You will get your new folks with depression who you think would be interested in participating in the study. Then, you will do the Welcome to WILLOW discussion with them and if they are interested in participating, please ask for their permission to share their contact information with the research team. If they say yes, you can either give me a call directly to convey their name, email, and phone number or you can complete our online referral form, which I will include in the email I'll be sending shortly. It is important that we do not share any of the patient's personal information via email. If they say no, that they do not want you to provide us with their contact information, you can give them my phone number or the patient flyer and they can call us directly. We will then take it from there to get them screened and enrolled. If after 6 weeks you are unable to find patients on your caseload who are interested and/or appropriate for the study, we will contact you to discuss ending your participation in the study or to provide additional support if you would like to continue with your participation.

Do you have any questions?

### **First Session (Both WILLOW and CAU)**

After the patients have been screened, you will schedule your session with the patient as you normally would. This first session will be the intake session during which you will do one last check to ensure the patient is eligible and appropriate for the study.

Exclusion criteria include:

- If the patient is experiencing active mania or psychosis
- If the patient meets criteria for alcohol or other drug abuse/dependence

## WILLOW Full RCT Therapist Protocol

- If the patient is deemed to be at imminent risk of suicide
- If the patient had an occurrence of self-harm or self-injury in the past 30 days

If the patient is deemed ineligible, you can have a conversation with your patient and your clinic about the next steps and let us know of the outcome.

If the patient is deemed eligible, please let us know and continue with therapy.

Do you have any questions?

A couple more things before we wrap up, It is important for our research that you keep track of your visits with each of your study. Please refrain from talking in detail about the research with others at your clinic who are participating in this study, especially if they are not in the same study condition as you are. *[explain if they are in CAU they should refrain from talking about the study with WILLOW therapists and vice versa]*.

Great, that's everything I had for you today! I will send you a follow up email reviewing some of the information we talked about. We are really excited to have you on board!

Thanks,  
Have a great day!

---

## Step 10: Post-Orientation Call Tracking

6. Send [Ready](#) to Accept Study Patients email for CAU
7. Send [Ready to Accept Study Patients email](#) for WILLOW (make sure to include the tracking sheet, and WILLOW User Guide)
8. Log date orientation completed
9. Log call in coversheet, including answers to any follow-up questions you had when confirming eligibility, and any concerns they brought up and how they were/will be addressed.

---

## Step 11: Post-Intake Steps

10. If the therapist doesn't get back to you within 24 hours of the intake session, send email to check if the patient was eligible or not.
11. Log the following info:
  - a. If patient showed up or not
  - b. Date rescheduled if patient didn't show up
  - c. Eligibility status
  - d. If patient is eligible, schedule ALL therapist assessments and record in Summative Tracking DB

## **Step 12: Scheduling Call**

1. Make scheduling call as soon as you can after first Tx session date, script below
2. If the therapist doesn't answer the call, send scheduling email and leave the voicemail below.
3. Call back/email every 2 days until you reach therapist.

### **VoiceMail Script:**

Hi \_\_\_\_\_, this is \_\_\_\_\_ from Evidence-Based Practice Institute. We wanted to check-in regarding your first session and to schedule your 4, 8, and 12 week study surveys. At your earliest convenience, please give us a call back at (Phone#)\_\_\_\_\_. Thanks!

4. If they call you back
  - a. And it is a good time for you to talk: Go through the script below
  - b. And it is not a good time for you to talk: Schedule a time you can call them back.
    - i. Log call time and date in the Pilot RCT Calendar
  - c. Log the call in the cover sheet

If they pick up, use the script below:

### **Call Script:**

Hi \_\_\_\_\_, this is \_\_\_\_\_ from Evidence-Based Practice Institute. Thanks again for your participation! I am calling today to schedule your study surveys. Is now a good time to talk?

In this call, I want to talk about your sessions with your patient \_\_\_\_\_. Since we cannot disclose your patient's name through email, if we need to talk about him/her I will use their study ID in place of their name which is \_\_\_\_\_.

Great! Firstly, I want to make sure we have the correct dates recorded for your patient. We have it that you completed your first session with the client, a Welcome/Get to know you, non-study session on DATE. In this session, you would have assessed to ensure that the client is appropriate for the study and could also be considered the intake session at some clinics. Is this date correct? (if not, correct date). Next, we have it that your first study session is DATE. Is this correct?

Fantastic! Thanks for reviewing that with us. Now we have three sets of surveys to schedule that will specifically focus on your participation in the study with your patient \_\_\_\_\_. The week 4 and 8 surveys will take about 20-30 minutes over the phone and the week 12 survey will take about an hour total. The first appointment will be 4 weeks from now, during the week of (Month, Date). Do you have a day or time that works best for you? And now your 8 week set of surveys: during the week of (Month, Date). Do you want to try to schedule for (Day) again? Great! Now your final set of surveys during the week of (Month, Date).

## WILLOW Full RCT Therapist Protocol

I also want to clarify your patient's Care Start Date. The Care Start Date is the first date the patient received services at your clinic and includes the intake session. So if your client has been to your clinic before, their Care Start Date is whatever day they first came in to receive services at your clinic. The care start date is your patient's first face-to-face psychotherapy session. With that in mind, what is the Care Start Date of patient \_\_\_\_\_?

Do you have any questions for me before we hang up? Great! I will send you an email listing these appointment times after we get off the phone. Have a good day!

---

### On Fridays, take these extra steps:

- Check all other daily folders for any stragglers (cover sheets that are not in the proper folder). Follow up as needed and place participant in appropriate folder
- Review the Pending folder and look at each tracking sheet to determine what is needed for each participant. Sort them accordingly.
- Move all of the participants in the Friday folder to either the pending folder, if everything is complete, or into daily folders for next week, depending on what action steps are required for that participant during the week.
- Send a reminder email to all therapists that have their assessment next week

---

### Step 13: Week 4 & 8 Assessments

1. Prepare Semi-Structured Interview notes form:
  - Open [interview notes template](#), save as 'SSID.4WeekSemi-StructuredInterview\_p#' or 'SSID.8WeekSemi-StructuredInterview\_p#'

#### Call Script:

Hi \_\_\_\_\_, this is \_\_\_\_\_ from Evidence-Based Practice Institute. Thanks again for your participation! I am calling today for your <<4 week or 8 week>> study assessment. Is now still a good time to talk? Great! I expect this call will take about 20-30 minutes to complete.

Remember, during this time we'll be talking only about your experience in the study you're your client <<NAME, SSID>>.

Any questions before we begin?

First, I want to personally thank you for the time you have invested into our study and your important contributions. We'd like to ask you several questions about your experience.

<<Administer Semi-Structured Interview, taking detailed notes during conversation >>

## WILLOW Full RCT Therapist Protocol

<<If needed, remind WILLOW therapists that they can they can use WILLOW with non-research clients (i.e., create WILLOW account) and that the patients can login to WILLOW at any time to complete their measures>>

Thank you for answering those questions! Is there anything else I should note about your experience in the study? Thank you.

Thank you so much for answering those questions! Now, I will send you the link to the Week \_\_\_ surveys for you to complete when you have a moment after our call today. You will need to enter your study ID and the study ID of your client. They are xxxx and xxxxx, I have included these in the email. If you run into any problems, please give me a call directly.

Our next study call is scheduled for Day, Date, Time. We'll send you a reminder the week before your next call. Thank you!

## Step 14: Week 12 Assessment

1. Prepare Semi-Structured Interview notes form:
  - o Open [interview notes template](#), save as 'SSID.4WeekSemi-StructuredInterview' or 'SSID.8WeekSemi-StructuredInterview'

### Call Script:

Hi \_\_\_\_\_, this is \_\_\_\_\_ from Evidence-Based Practice Institute. Thanks again for your participation! I am calling today for your 12 week study assessment. Is now still a good time to talk? Great! I expect this call will take about 30 minutes to complete.

1. Administer Semi-Structured Interview, taking detailed notes during conversation
  - <<If needed, remind WILLOW therapists that they can they can use WILLOW with non-research clients (i.e., create WILLOW account) and that the patients can login to WILLOW at any time to complete their measures>>
  - o Send link to Week 12 surveys via email

Thank you so much for answering those questions! I have just sent you the link to the Week 12 surveys. You will need to enter your study ID and the study ID of your patient. They are xxxx and xxxxx, I have included these in the email. This is your final appointment for this patient! Once you are completed with the survey, I will go ahead and process your payment which will be a \$60 check. Do you have any final questions for me before I let you go to do the survey? Thank you!

## **Step 15: After 6 weeks and no patient referral**

1. Call provider to discuss either discontinuing participation or how we can provide additional support if they would like to continue with participation

## **Step 16: End of Study Procedures**

1. Create WILLOW accounts for CAU therapists at the end of study and provide them the WILLOW training materials we give all new therapists, because CAU therapists will get free access to WILLOW for 12 months if they successfully recruited 1 study patient.
2. When the therapist's last patient completes their participation, log the date of completion as the start date and 12 months after that date as the end date in the following log for both WILLOW and CAU therapists.

PracticeGround: Transforming Training and Delivery of Mental Health EBPs

NCT02314624 | Statistical Analysis Plan | February 8, 2020

Analysis Strategy

We conducted all analysis in IBM SPSS V19. We used the Generalized Linear Model to examine the between-condition change over time on study outcomes. The effects of primary interest were those reflecting the effects of WILLOW. For outcomes measured at baseline and follow-up points, that was the Time X Condition effects (measuring between-condition change from baseline). For outcomes measured only at follow-up points (e.g., therapeutic alliance and use of evidence-based therapy tasks), that was the Condition effects since they would represent average between-condition differences during the time patients received services. As previously mentioned, providers completed questionnaires for each study patient they treated. Hence, the provider sample size reflects the number of patients they answered about, not the number of providers. Several providers participated in the study concurrently with multiple patients. Patients were included in the analyses only if they attended five or more sessions with a participant provider.

Preliminary analyses provided important information guiding our strategy. First, we found no statistically significant differences between conditions on baseline measures. Second, we computed the design effects due to this nested design to determine the extent to which the intraclass correlation due to clustering and size of the cluster affected the analyses. Design effects ranged up to 1.8. Because all were under 2.0, we did not adjust analyses to account for clustering effects (Muthén & Satorra, 1995). For providers meeting participating in both studies, we used their Study 1 data for outcomes except for outcomes measured only in Study 2. For those outcomes, we used their Study 2 data.

References

Muthén, B.O. & Satorra, A. (1995). Complex sample data in structural equation modeling. *Sociological Methodology*, 25, 267-316. doi: 10.2307/271070

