**If there are no questions, move on to the next section**

### **Describe Surveys:**

Four times during the 12-week study you will be asked to complete some questionnaires online.

- The first time will be today after we finish with our call. I will be sending you the links to our online consent form and also the link to the first set of surveys for you to do.
- As a kind of addendum to today's surveys, I'll also be sending you a link to a really quick survey for you to do after your next session.

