### **Ask them the date for the next session and record in coversheet**

- If you're able to complete your first set of surveys today [before next session], then I'll go ahead and send you that link to the quick survey for you to do.
- Now, the next three times we'll ask for you to complete surveys will be at Weeks 4, 8, and 12 during your participation. These will take between 45-60 minutes to complete and will involve a 10-15 minute phone call with a member of our research team and then an online survey that will take about 30 minutes answering questions about your mood, your satisfaction with the treatment you are receiving, and questions about your experience with your therapy and therapist.

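### The SAP names no model for correlation between a patient's repeated surveys; read as written, the standard errors for both effects of primary interest are wrong

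*SAP*

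**What the plan says.** The Patient Protocol (Step 3, Describe Surveys) tells patients: "Four times during the 12-week study you will be asked to complete some questionnaires online". The first set is at baseline, and the later "surveys will be at Weeks 4, 8, and 12 during your participation". The Therapist Protocol (Steps 6 and 7) has therapists complete surveys at the same three follow-up weeks for each study patient.

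The SAP (Analysis Strategy) uses these repeats: "We used the Generalized Linear Model to examine the between-condition change over time on study outcomes". Two effects are of primary interest. For outcomes with a baseline it is Time X Condition. For outcomes collected only at follow-up, such as alliance and use of evidence-based tasks, "that was the Condition effects since they would represent average between-condition differences during the time patients received services".

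The SAP's only remarks on correlated data concern the nested design, straight after it notes that providers treated several patients: "Design effects ranged up to 1.8", and because all were below 2.0, "we did not adjust analyses to account for clustering effects". It says nothing about correlation between one patient's surveys.

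**The concern.** In its standard form a generalized linear model assumes independent observations. Surveys from one patient over 12 weeks are unlikely to be independent, and the two tests that the SAP relies on respond differently.

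- **Condition, follow-up-only outcomes.** The effect averages up to three surveys per patient. Positive correlation means that these carry less information than three independent rows, so the standard error is too small and the test rejects too often.
- **Time X Condition.** The effect is a within-patient change. Positive correlation partly cancels in a difference. A model that ignores it usually makes the standard error too large, and real differences in change can be missed.

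No single inflation factor corrects both tests. A provider effect alone would not model the correlation among one patient's surveys either, so this is a separate matter from provider clustering.

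**Working it through.** **The plan's own figure.** The only relevant figure is the design effect of up to 1.8. With DEFF = 1 + (m − 1) × ICC and the 2 to 5 patients per therapist requested in the Therapist Protocol (Step 2), a value of 1.8 needs an ICC of 0.80, 0.40, 0.27 or 0.20 for m = 2, 3, 4 or 5. The SAP gives neither m nor ICC, so 1.8 cannot be reproduced. It concerns patients within providers and does not settle the question here.

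**Inputs.** From the documents: up to four surveys per patient for Time X Condition and up to three for Condition. Assumed, because the documents give none: within-patient correlation r = 0.3 / 0.5 / 0.7, two-sided alpha 0.05, and 80% power under a correct model as the reference (1.96 + 0.84 = 2.80 standard errors). All results below suppose that rows were analysed as independent.

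**Condition over three surveys.** With equal correlation, the true variance of the average is 1 + 2r times the assumed variance, that is 1.6 / 2.0 / 2.4. True type I error is 2 × [1 − Φ(1.96 / √(1 + 2r))]:
- r = 0.3: 1.96 / √1.6 = 1.55, giving 12.1%
- r = 0.5: 1.96 / √2.0 = 1.39, giving 16.6%
- r = 0.7: 1.96 / √2.4 = 1.27, giving 20.6%

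Under AR(1), with r the correlation between adjacent surveys, the multiplier is 1 + (4r + 2r²)/3 = 1.46 / 1.83 / 2.26. The same formula gives 10% / 15% / 19%, so the inflation does not hinge on equal correlation.

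**Time X Condition, baseline to Week 12.** The true variance of the change is (1 − ρ) times the assumed variance, where ρ is the correlation between baseline and Week 12. Power is Φ(2.80 − 1.96 / √(1 − ρ)).

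| r | ρ, equal correlation | Power | ρ = r³, AR(1) | Power |
|---|---|---|---|---|
| 0.3 | 0.3 | 68% | 0.027 | 79% |
| 0.5 | 0.5 | 51% | 0.125 | 76% |
| 0.7 | 0.7 | 22% | 0.343 | 65% |

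**Time X Condition, linear time over four surveys, AR(1).** With weights −1.5, −0.5, 0.5, 1.5, the variance ratio is (5 + 2.5r − 3r² − 4.5r³)/5 = 1.07 / 0.99 / 0.75. Type I error is 5.8% / 4.9% / 2.3% and power is 82% / 80% / 70%. At r = 0.3 the test is slightly liberal.

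**Simulation check** (3000 runs; 40 patients per arm assumed, since the documents give no sample size).
- Equal correlation: Condition type I error was 13.1% / 17.7% / 21.9%. Time X Condition power with linear time was 68% / 51% / 23%.
- AR(1): Time X Condition type I error was 6.8% / 4.8% / 3.2% with linear time and 3.5% / 1.4% / 0.4% with time as a factor.
- A test on per-patient slopes, which takes the patient as the unit, had type I error of 4.3% to 6.0% across the scenarios. Its power under equal correlation was 78% to 79%.

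**The case against.** The strongest objection is that the SAP never says rows were treated as independent. The name could stand loosely for a GEE extension or a repeated-measures model. The SAP also counts the provider sample by patients answered about, not by questionnaires, which hints at the patient as the unit. This stands as a limit: independence is an inference from what the text leaves out. It does not clear the SAP. Independent rows are what the named model implies, and a reader would have to supply any other structure.

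A second objection is that the loss of power depends on the correlation structure and on how time is coded, and the SAP states neither. This also stands. The large losses belong to equal correlation; under AR(1) they are smaller, and with linear time they can disappear.

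Three stronger readings are tempting but not supported:
- A reader might take the statement that clustering was not adjusted for as proof that repeated surveys were ignored. In context it concerns providers with several patients and does not show how surveys within a patient were handled.
- A reader might infer that results lean towards WILLOW on process measures. An understated standard error inflates two-sided rejection symmetrically, so false positives can favour either arm.
- A reader might multiply the 1.8 by 1 + 2r. That needs 1.8 to be a design effect for per-patient averages. The SAP gives no unit for it, and if it came from pooled survey rows it may already contain some within-patient correlation.

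**Conclusion.** The point holds as a defect of specification with consequences for inference. If the named model was fitted as named, the Condition test over three surveys has a type I error of about 12% to 21% under equal correlation of 0.3 to 0.7, and about 10% to 19% under AR(1). The Time X Condition test is usually too conservative. How much power it loses ranges from most of it (80% to 22% at r = 0.7, equal correlation) to none (linear time, AR(1), r of 0.5 or less).

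All these sizes rest on assumed correlations, two-sided 0.05 and an 80% reference. The documents supply no correlation, sample size, alpha or power. If a model for repeated measures was in fact fitted, the p-values may be sound, but the SAP then misnames the model and omits what is needed to reproduce or judge it.

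**What to change.** Replace the sentence that names the model with one of two specifications:

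- (a) a mixed model suited to the outcome type, with Condition, categorical Time and Condition x Time, an unstructured within-patient covariance over surveys, and a provider random effect; or
- (b) a GEE with the same fixed effects and robust standard errors clustered on provider, without a random effect.

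Use the same approach for the Condition test of follow-up-only outcomes over Weeks 4, 8 and 12, and re-run both sets of tests. If a GEE or repeated-measures model was already used, correct the name and state its covariance or working correlation, how time was coded and how standard errors were obtained.

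The cost is a change of SAP wording and a re-run on existing data; no new data are needed. Some Condition p-values may become larger. Under (b), the number of providers should be reported, because robust standard errors need a small-sample correction when clusters are few.
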